#### 8.7.1.4. SERIOUS ADVERSE EVENTS

Serious adverse events (SAEs) are those events recorded as 'Serious' on the Adverse Events page of the eCRF. A summary of serious TEAEs by SOC and PT will be prepared.

#### 8.7.1.5. ADVERSE EVENTS LEADING TO DEATH

TEAEs leading to Death are those events which are recorded as 'Fatal' on the Adverse Events page of the eCRF. A summary and listing of TEAEs leading to death by SOC and PT will be prepared.

#### 8.7.1.6. ADVERSE EVENTS OF SPECIAL INTEREST

Adverse Event of Special Interest (AESI), as defined in section 8.4.6 of the protocol, are those events recorded as 'AESI' on the Adverse Events page of the eCRF.

AESIs include haemolysis and methemoglobinemia.

Haemolysis is defined as at least three of the following four laboratory parameter criteria fulfilled (high and low refers to the upper and lower reference limits from the central lab):

- a) Low haemoglobin OR haematocrit
- b) Low haptoglobin
- c) High reticulocyte count
- d) High indirect (unconjugated) bilirubin

Methemoglobinemia is defined as both the following two criteria fulfilled:

- a) Methemoglobin reading by pulse oximetry >2% and
- b) Methemoglobin by blood test > ULN

Note: If pulse oximeter is not available or can't be used, the blood test value will be used alone to meet AESI reporting criteria.

A summary of AESIs by SOC and PT will be prepared. The proportion of participants with prespecified events listed as AESIs during the on-treatment period will be provided. All AESIs will be included in the summary table, even if the incidence is zero.

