 - a) Have tested positive for severe acute respiratory syndrome-related coronavirus-2 (SARS-CoV-2) based on a validated test per local guidelines at Screening and Baseline
 - b) Have to comply with quarantine requirements per local Public Health directive

Note: Participants with clinical symptoms suggestive of COVID-19 can be rescreened after 14 days if symptoms resolve and the participant does not test positive for SARS-CoV-2.
19. Has been vaccinated with live or live-attenuated virus vaccine within 30 days prior to Screening.

Diagnostic Assessments

20. Has an uncontrolled hypertension as diagnosed by participant's treating physician.
21. Has any of the following abnormal laboratory values at Screening
 - a) Alanine aminotransferase (ALT), Aspartate aminotransferase (AST), Gamma glutamyl transpeptidase $>2 \times$ upper limit of normal (ULN), Alkaline Phosphatase $>1.5 \times$ ULN, provided cholestatic or other liver disease is excluded
 - b) Total bilirubin (TBL) >1.0 ULN (participants with Gilbert's syndrome can be enrolled if other liver function tests are within stated limits)
 - c) Impaired renal function as indicated by estimated glomerular filtration rate <30 mL/min/1.73 m² (CKD-EPI 2009 calculation)
 - d) Hemoglobin <10 gm/dL, white blood cell count <2500 mm³, neutrophil count <1500 mm³, platelet count $<100 \times 10^3$ /mm³.

Lifestyle

22. Based on the known metabolism of OG-6219 there are no effects of alcohol, caffeine, or tobacco associated with study treatment. However, during the study participants are asked to refrain from:
 - a) Excessive tobacco use and smoking CCI [REDACTED] based on Investigator's discretion).
CCI [REDACTED]
 - b) Active use of illicit drugs and/or alcohol abuse/dependence, as determined by the Investigator.

Note: Alcohol intake should be limited to 2 to 3 units per day, not to exceed 14 units per week.
23. Has a prior or current history of drug or alcohol abuse disorder according to Diagnostic and Statistical Manual of Mental Disorders 5 (DSM5).⁶⁶

Prior/Concurrent Clinical Study Experience

24. Has undergone blood transfusion within 2 weeks of V1. In addition, has lost ≥ 1 unit of blood (approximately 300 mL) within 8 weeks before the first dose of OG-6219.
25. Use of treatments that might interfere with the conduct of the study or interpretation of the results ([Appendix 7](#)).

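### AESI counts rest on the investigator's eCRF flag alone: the SAP plans no count of its own haemolysis and methemoglobinemia criteria from the data and no reconciliation with the flag

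*SAP*

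**What the plan says.** SAP 8.7.1.6 identifies AESIs for analysis by source: they "are those events recorded as 'AESI' on the Adverse Events page of the eCRF". It then defines the two named events by measurement.

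- **Haemolysis:** "Haemolysis is defined as at least three of the following four laboratory parameter criteria fulfilled". The four are low haemoglobin or haematocrit, low haptoglobin, high reticulocyte count and high indirect bilirubin, each judged against the central laboratory's limits.
- **Methemoglobinemia:** two conditions, both required: "Methemoglobin reading by pulse oximetry >2% and" "Methemoglobin by blood test > ULN". An exception follows: "If pulse oximeter is not available or can't be used, the blood test value will be used alone to meet AESI reporting criteria".

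The planned outputs are a summary by system organ class and preferred term, and this: "The proportion of participants with prespecified events listed as AESIs during the on-treatment period will be provided". AESI rows are printed even when nothing was recorded.

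Elsewhere the SAP does count safety thresholds from the data. Section 8.7.2.2 tabulates liver criteria from post-baseline results, including a combined transaminase and bilirubin (or INR) criterion. Section 8.7.3 counts participants by QTcF limits.

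**The concern.** The definitions could be applied by program, but the count depends on someone at the site recognising the pattern and setting a flag. Haemolysis is the harder pattern to see: it is a composite of four parameters, and each may be only slightly outside its limit. Safety is a primary objective, and these are the AESIs that the SAP names. A reader of the study report will take a zero or low AESI row as evidence about the drug, when it may partly reflect how completely sites set the flag.

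The methemoglobinemia criteria raise a separate question of uniformity. Two participants with the same raised blood value can be classified differently because of the equipment at hand, and no planned output shows how many cases arose under each route.

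**Working it through.** The documents state no AESI rate, capture rate or detection probability, so there is no figure of theirs to reproduce. The check is mainly of the text.

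**Step 1. Does another planned output give the by-arm count of the haemolysis composite?**

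| Output | What it shows | By-arm count of participants meeting 3 of 4? |
|---|---|---|
| AESI table (SAP 8.7.1.6) | Events flagged on the eCRF | Only if flagged |
| Laboratory shift tables (SAP 8.7.2) | Each parameter separately, by visit | No |
| By-visit summaries (SAP 8.1.4) | Scheduled time points only | No |
| Listings (SAP 8.1.1, 8.1.4) | All values, including unscheduled | No; values only |

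An unscheduled sample taken to investigate suspected haemolysis would reach the listings but not the by-visit summaries.

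**Step 2. Which blood-positive participants meet the methemoglobinemia criteria?**

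| Blood methemoglobin | Oximeter | Criteria met? |
|---|---|---|
| Above ULN | Usable, reads above 2% | Yes |
| Above ULN | Usable, reads 2% or less | No |
| Above ULN | Not available or not usable | Yes |

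Let *h* be the share of blood-positive participants with a usable oximeter, and *s* the share of those whose oximeter reads above 2%. Both are assumed. The fraction of blood-positive participants who qualify is 1 − *h*(1 − *s*).

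| *s* | *h* = 0 | *h* = 0.5 | *h* = 1 |
|---|---|---|---|
| 0.5 | 1.00 | 0.75 | 0.50 |
| 0.7 | 1.00 | 0.85 | 0.70 |
| 0.9 | 1.00 | 0.95 | 0.90 |

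The fallback without an oximeter is the more inclusive route. Blood-positive participants fail to qualify only where a usable device reads 2% or less.

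**Step 3. What could incomplete flagging do to one arm?** The group size of 95 is from SAP 4.3. Assume true incidence *p* and probability *c* that a case is flagged. Expected recorded cases are 95*pc*, and P(at least one recorded) = 1 − (1 − *pc*)^95.

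| *p* | *c* = 100% | *c* = 75% | *c* = 50% |
|---|---|---|---|
| 1% | 0.615 | 0.511 | 0.379 |
| 3% | 0.945 | 0.885 | 0.762 |
| 5% | 0.992 | 0.974 | 0.910 |

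For example, at *p* = 1% and *c* = 50%: 1 − (1 − 0.005)^95 = 0.379, with 95 × 0.005 = 0.48 expected recorded cases against 0.95 at full capture. Incomplete flagging matters most when the event is rare.

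**The case against.** The strongest reply is that other safeguards exist and part of the evidence is hidden. Protocol 8.4.6 requires every AESI to be entered as an AE. Appendix 4 describes ongoing monitoring and immediate notification. Appendix 3 makes investigators document their review of each laboratory safety report, and the DMC reviews AESIs (Protocol 2.3.1). The specific AESI text in 8.4.6 is blacked out and may contain laboratory alerts, confirmation steps or a baseline condition. Taking AESIs from the AE page also matches how the SAP handles serious and fatal events.

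Much of this stands. Missing here means missing from the AESI table, not unseen in the trial, and nothing is shown about the redacted protocol text. But these safeguards support reporting by sites; none is a count from the data. Protocol 8.3.7 treats a laboratory change as an AE when it leads to a change in medical care, so a mild composite could be left unflagged unless the redacted text says otherwise. Serious and fatal events are not defined by laboratory limits, so that parallel is weaker than the one with liver and QTcF.

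A reader might infer three stronger things that the documents do not support.

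- *That lack of an oximeter loses cases.* Step 2 shows the reverse.
- *That abnormalities present before dosing inflate the AESI table.* Protocol 5.2 bars haemoglobin only below 10 g/dL, and "participants with Gilbert's syndrome can be enrolled if other liver function tests are within stated limits". If the laboratory's lower haemoglobin limit is above 10 g/dL (an assumption), two of the three required criteria could be present at entry. But a table built on flags gains nothing from this unless an investigator reports an event, and SAP 8.7.1 excludes pre-treatment events from the treatment-emergent analyses unless they worsen or become serious. The point bears on how a programmed count should be built.
- *That the comparison with placebo is biased towards no difference.* No AESI test is planned, the trial is double-blind, and nothing in the documents fixes a direction.

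**Conclusion.** The concern holds for the visible SAP text, as a gap in analysis and reporting. For haemolysis, the flag is the only planned route to a by-arm count of a composite that could be derived from measured values. For methemoglobinemia, which rests on oximetry as well as a blood test, the criteria combine two case definitions and no split by route is planned.

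The size cannot be estimated from the documents. The incidence, capture and oximeter shares above are assumed, and they show only that the effect ranges from negligible with complete flagging to material for a rare event with incomplete flagging. This is a worthwhile, inexpensive improvement rather than a demonstrated error, and it does not touch the primary efficacy analysis.

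**What to change.** In SAP 8.7.1.6, keep the investigator-flag table and add a supportive programmed table by arm for the SAF. Use all available post-baseline samples, including unscheduled ones, and show:

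1. Participants meeting at least three of the four haemolysis criteria on the same sample date: (a) with the composite not already met at baseline and, separately, (b) with at least one criterion new since baseline.
2. Where measured, participants with blood methemoglobin above ULN, split by whether an oximeter reading was available and, if so, whether it exceeded 2%.

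Add a listing of every discordance between the derived cases and the eCRF flag, in both directions, for query before database lock.

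The cost is one SAP paragraph, one table and one listing, plus some laboratory-only positives to explain in the report. Protocol Appendix 3 visibly includes haemoglobin, haematocrit, reticulocytes and unconjugated bilirubin. The schedules for haptoglobin and methemoglobin cannot be seen because of redaction, so the sponsor should confirm who was measured and when, and state the denominators. No clinical definition or site procedure changes.

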### 8.7.2. Laboratory Evaluations

Quantitative laboratory measurements reported as '< X', i.e., below the lower limit of normal (LLN), or '> X', i.e., above the upper limit of normal (ULN), will be converted to X for the purpose of quantitative summaries, but will be presented as recorded, i.e., as '< X' or '> X' in the listings. If local and central laboratory assessments are available from the same day, central laboratory assessments will be used in the summary.

The following summaries will be provided for laboratory data:

- Observed values and change from baseline by visit for Chemistry, Hematology and Urinalysis (quantitative measurements)
- Observed values for categorical measurements
- Shift from baseline value to each post-baseline visit value according to normal range criteria (quantitative measurements and categorical measurements)

#### 8.7.2.1. LABORATORY REFERENCE RANGES

Quantitative laboratory measurements will be compared with the relevant laboratory reference ranges in SI units and categorized as:

- Low: Below the lower limit of the laboratory reference range.
- Normal: Within the laboratory reference range (upper and lower limit included).
- High: Above the upper limit of the laboratory reference range.

#### 8.7.2.2. LIVER FUNCTION RELATED CRITERIA

Summary details for liver enzyme abnormalities will be presented by treatment group and assessed by using post-baseline results for Alanine Aminotransferase (ALT), Aspartate Aminotransferase (AST) and Total Bilirubin (TBL) given an upper limit of normal (ULN):

- ALT or AST  $>8 \times$  ULN
- ALT or AST  $>5 \times$  ULN
- ALT or AST  $>3 \times$  ULN and TBL  $>2 \times$  ULN or international normalized ratio  $>1.5$
- ALT or AST  $>3 \times$  ULN

### 8.7.3. ECG Evaluations

The following ECGs measurements will be reported for this study:

- Axis (degree)
- Heart Rate [beats per minute (bpm)]
- PR Interval (msec)
- QT Interval (msec)
- QTcB Interval (msec)
- QRS Interval (msec)
- RR interval (msec)
- QTcF Interval (msec)
- Overall interpretation of ECG:
  - Normal
  - Abnormal, Not Clinically Significant (Abnormal NCS)
  - Abnormal, Clinically Significant (Abnormal CS)

Triplicate standard 12-lead ECGs will be obtained after the participant has been in a supine position for at least 5 minutes. ECG measurements will be summarized by taking the average of the available assessments.

The following summaries will be provided for ECGs data:

- Observed values and change from baseline by visit and timepoint
- Shift in normal/abnormal NCS/abnormal CS in the overall interpretation from baseline to each timepoint

The number of participants with absolute QTcF values CCI, and the number of participants with change from baseline in QTcF, CCI during

treatment will be summarized by treatment group. QTcF prolongation is defined as CCI or a change CCI.

A scatter plot will be presented, showing baseline QTcF on the x-axis, post-baseline QTcF on the y-axis (one panel for each treatment), and diagonal lines indicating changes of -60, -30, 0, +30, and +60. Different symbols will be used to identify the different post-treatment timepoints.

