- k. Participant compliance with eDiary entries must be CCI during both the SC and the BC to be randomized (information to be provided by the eDiary portal).
- l. CCI
- m. ECG will be performed pre-witness dose and 1.5 hours after dose (witness dose), following the PK Sparse assessment.
- n. CCI
- o. If indicated, participants will be tested for gonorrhea and chlamydia unless they were screened within the past 3 months and have no new sexual partner. Testing for trichomonas and bacterial vaginosis will only be required if abnormal vaginal discharge is present. Testing will be performed locally and may be repeated during the study as needed.
- p. If local regulations indicate that UPT should be performed more frequently, follow local regulations where applicable.
- q. In addition to visits specified, serum pregnancy test also required any time pregnancy is suspected or if UPT is positive (unless pregnancy already confirmed by ultrasound).

CCI

- u. OG-6219 and active metabolite FOR-1011; blood samples for PK analysis will be collected at all visits during the dosing period including the EOT Visit and discontinuation. In addition, for the optional intensive PK sampling, a minimum of C participants per treatment group (incl. Placebo group) will be enrolled on CCI, for entire duration of the study. A complete schedule of PK assessment times is found in Table 8. The witness dose should be administered at site for CCI.

- v. **C** sample collection to be collected within 12±4 hours of last dose of study medication. If not possible, the PK sample should be collected at **C** irrespective of the timing of the last study dose taken.

CCI

- y. Based on determination of positive C-SSRS results for suicidality, the participants will be discontinued from the study medication and referred to a specialist at the Investigator's discretion for further evaluation. In addition, the positive results from C-SSRS evaluation will have to be treated as an SAE and reported to the Sponsor in a timely manner.

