OG-6219 and FOR-1011 displayed inhibition of the hERG channel potassium current with half maximal inhibitory concentration (IC₅₀) values of CCI, respectively, indicating a potential risk of QTc prolongation. Both compounds are however highly bound to plasma proteins, resulting in low free concentrations in vivo and no cardiovascular toxicity or effects on ECG were observed in the in vivo cardiovascular safety study in cynomolgus monkeys. No clinically significant ECG changes were observed in Phase 1 with intense monitoring. To manage the risk of a proarrhythmic activity, in the Phase 2a/b study, ECG recordings at Screening aim to identify and exclude participants with clinically significant cardiac abnormalities. The International Council for Harmonisation of Technical Requirements for Pharmaceuticals for Human Use (ICH) E14 Clinical Evaluation of QT/QTc Interval prolongation and proarrhythmic potential and non-antiarrhythmic drug recommends that ECG recordings be performed at time points of expected C_{max}. Therefore, ECG recordings and vital sign measurements will be performed at CCI

CCI [REDACTED] at each subsequent visit until the End of Study (EOS).

CCI [REDACTED]

[REDACTED] The ultraviolet (UV) absorbance of OG-6219 has a local maximum close to the low end of the natural sunlight wavelength range resulting in molar extinction coefficients values higher than the limit value of 1000 at wavelengths in the UVB spectrum below 305 nm. The penetration of UVB light into human skin is mainly limited to the epidermis and the clinical relevance of photochemical activation by UVB is therefore considered less important than activation by UVA for systemic drugs. The molecular structure of OG-6219 has been evaluated in silico with no alerts for photo-induced genotoxicity, chromosome damage, or photomutagenicity. In addition, no relevant distribution of OG-6219 to the skin or eyes was observed in a pre-clinical study in albino animals. Although, the binding affinity of OG-6219 to melanin has not been evaluated, the risk for phototoxicity of OG-6219 is considered minimal based on the totality of the available data and no specific precautions are therefore warranted.

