2.3.3 Overall Benefit Risk Conclusion

Current medical treatments for ERP provide similar, suboptimal pain control and have safety and tolerability issues that limit their use, often leading patients to have repeated surgical interventions. Thus, there is a need for development of new ERP medical therapies. A local inhibition of estrogen production at the ectopic implants level, for treatment of ERP, such as OG-6219, an oral, potent, selective inhibitor of HSD17 β 1 which can avoid the systemic adverse impact of hormonal treatments.

OG-6219 is a novel HSD17 β 1 enzyme inhibitor being developed for the treatment of moderate to severe ERP. The pharmacological action of OG-6219 is based on its potent and selective binding to HSD17 β 1 and ability to locally inhibit E2 production. The Phase 2a/b PoC and dose-range study aims to assess the efficacy, safety, and tolerability of 3 dose levels of OG-6219 on ERP (CCI BID). Phase 1 data demonstrated pharmacologically relevant endometrial exposure in healthy pre-menopausal participants at 2 higher doses tested (CCI BID and CCI BID). The lower doses of CCI BID are planned based on Phase 1 PK modeling data. CCI

OG-6219 was found to be safe and well-tolerated in Phase 1 with exposure of a total of 71 participants, of which 37 participants were pre-menopausal; 10 pre-menopausal participants were treated with the highest dose of 150 mg BID for 14 days during the first half of the menstrual cycle. No serious or severe AEs were reported. CCI

CCI [REDACTED]
[REDACTED]
[REDACTED]
[REDACTED] In the Phase 2a/b study, participants will be randomized to be treated with 3 dose levels of OG-6219 (CCI [REDACTED] BID), or Placebo for approximately CCI [REDACTED] (up to C cycles, not longer than CCI [REDACTED] of study treatment exposure).

Most relevant pre-clinical findings that may be indicative of safety risks include hERG channel inhibition in vitro CCI [REDACTED] concentrations of both parent (OG-6219) and primary metabolite (FOR-1011), however, both OG-6219 and FOR-1011 are highly bound to plasma proteins resulting in low free concentrations in vivo and no pre-clinical nor Phase 1 evidence of QC prolongation has been found. CCI [REDACTED]
[REDACTED]

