8.3.3 Electrocardiograms

Triplicate standard 12-lead ECGs will be obtained after the participant has been in a supine position for at least 5 minutes at times indicated in the SoA (Section 1.3). The ECGs will be

measured using standardized equipment provided by a central core laboratory. The ECGs will be assessed by central review and a report provided to the site. Results from Screening ECG must be either normal or reveal findings deemed not to be of clinical significance by the Investigator for the participant to qualify for the study. CCI

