9.4.3 Secondary Endpoint Analysis

Secondary endpoints assessing change in continuous endpoints over time (either measurements within the cycle or at an individual visit) will use longitudinal models as described for the primary endpoint and/or ANCOVA models. Changes from SC to SFC will be compared using ANCOVA models in the SFAS. Select longitudinal models which focus on TRC1 and TRC2 may exclude TRC3 from the model. An unstructured error structure will be assumed for all longitudinal models. If nonconvergence is encountered, CS and AR (1) error structures will be considered.

Definitions corresponding to the incidence of clinically significant values will be provided in the SAP.

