5. To evaluate the change in the PGI-S Score at different time points	
 
Change in PGI-S Score from C to Phone Contact CCI
 

6. To evaluate the change in the PGI-C Score in different time points	
 
Percentage of participants with any improvement on the PGI-C at TRC1, TRC2, and TRC3
 

7. To evaluate the change in the EHP-30 domains (CCI ) from BC to TRC3	
 
Change from BC to TRC3 in the EHP-30 Domain Scores
 

Secondary Safety Endpoints	
8. To assess the incidence of clinically significant b changes from V1 to C in bone biomarkers: 	
 
Mean change from V1 to C in bone biomarker levels
 

9. To assess the incidence of any clinically significant b changes in laboratory parameters from V1 to CC 	
 
Proportion of participants with clinical parameters of significance from V1 to CCI
 

10. To assess vaginal bleeding pattern over the 3 menstrual cycles (TRC1, TRC2, and TRC3) as captured in the eDiary	
 
Mean change from BC to TRC1, TRC2, TRC3 in the number of days on period and number of days with irregular vaginal bleeding/spotting
 

11. To assess any potential change in the ECG parameters at CCI	
 
ECG parameter changes at CCI
 

Secondary PD / PK Endpoints	
12. To assess the change from CCI in serum hormone c concentrations	
 
Mean change from CCI in serum hormone levels
 

13. To assess any difference in serum hormone c concentrations at C between active treatment versus placebo	
 
Serum hormone levels at V5 comparing Group A (CCI BID), B (CCI BID), C (CCI BID) with Group D (Placebo)
 

Version Date: 09JUN2025

- Treatment Cycle 1 is the period between the first day of menses associated with treatment start (C) to the day prior to the first day of next menses, regardless of number of days.
- Treatment Cycle 2 is the period between the first day of second menses after end of BC to the day prior to first day of next menses, regardless of number of days.
- Treatment Cycle 3 or EOT is the period between the first day of third menses after end of BC to either end CCI on study treatment, whichever occurs first.

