### 8.1.3. Baseline and Change from Baseline

Baseline is defined as the last non-missing measurement (including unscheduled assessments) taken prior to first dose of randomized study medication (reference start date).

In the case where the last non-missing measurement and the reference start date coincide, that measurement will be considered pre-baseline with the following exceptions:

Adverse Events (AEs) and medications commencing on the reference start date will be considered as either pre-baseline or post-baseline based on the collected eCRF assessment of whether the item started prior to the start of study medication.

Visit 4 measurements scheduled to be made after first dose of randomized study medication (e.g. post-dose ECG measurements) will be regarded as post-baseline. Baseline ECG is the average of the triplicates taken prior to first dose of randomized study medication.

For related assessments (e.g., systolic and diastolic blood pressure), it is desirable that all baseline values come from the same measurement date and not from different dates/visits in case one value is missing. In the event where one value is missing, values from the same measurement dates will be used.

For HRQoL, Fatigue, and Productivity Questionnaires (EHP-30, EQ-5D-5L, WPAI-Endometriosis, PROMIS Fatigue Short Form 6a, and PGI-S) assessments collected on CCI will be considered Baseline. In case data were not entered CCI but within a few days from visit 4, these data will still be considered as baseline.

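### SAP 8.7.3 analyses ECG data only descriptively and prespecifies no baseline-adjusted dose-minus-placebo QTcF difference with a confidence interval, although QTc is a named risk and ECG change is secondary safety endpoint 11

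*SAP*

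**What the plan says.** **The risk.** Protocol 2.3.1 reports hERG inhibition by the parent drug and its main metabolite, "indicating a potential risk of QTc prolongation". Protocol 2.3.3 ranks it high: "Most relevant pre-clinical findings that may be indicative of safety risks include hERG channel inhibition in vitro". Both sections add that plasma protein binding is high and that neither the preclinical in vivo work nor Phase 1 showed QTc prolongation.

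**The measurement.** Protocol 1.3, footnote m: "ECG will be performed pre-witness dose and 1.5 hours after dose (witness dose), following the PK Sparse assessment". Protocol 8.3.3: "Triplicate standard 12-lead ECGs will be obtained after the participant has been in a supine position", with central reading. SAP 8.1.3: "Baseline ECG is the average of the triplicates taken prior to first dose of randomized study medication".

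**The objective.** Secondary safety objective 11 in SAP Table 1 (also protocol Table 1): "To assess any potential change in the ECG parameters at CCI", where the visits are blacked out. The matching endpoint is change in ECG parameters.

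**The analysis.** SAP 8.7.3 lists "Observed values and change from baseline by visit and timepoint", a shift table of the overall interpretation, counts of women beyond QTcF limits by treatment group, and a scatter plot of post-baseline against baseline QTcF with one panel per arm. SAP 8.1.1 adds box plots and defines continuous summaries as n, mean, SD, median, minimum and maximum.

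**The general rule.** Protocol 9.4.3: "Secondary endpoints assessing change in continuous endpoints over time (either measurements within the cycle or at an individual visit) will use longitudinal models", and/or ANCOVA. SAP section 10 declares no change from the protocol's planned analyses.

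**The concern.** The trial takes trouble to measure QTcF well: triplicate recordings, central reading, a time point near peak concentration and a concurrent placebo arm. The analysis plan then stops at within-arm summaries. A mean change from the pre-dose baseline to a reading 1.5 hours later, or at a later visit, contains any drug effect plus whatever would have changed anyway with time of day or visit. The placebo arm measures that second part, but no planned output formally subtracts it, adjusts for baseline QTcF or attaches an interval.

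At stake is how clearly the trial can speak about a risk that the sponsor itself names. For each dose, the useful statement is an estimated QTcF effect relative to placebo with limits around it. If that is produced only after unblinding, SAP section 2 requires it to be labelled as unplanned, and the model and key time points would be chosen with the data in view.

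**Working it through.** **1. Is a contrast planned anywhere?**

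| Place | ECG output | Placebo contrast or interval? |
|---|---|---|
| SAP 8.7.3 | Observed values and change, by visit and time point | No |
| SAP 8.7.3 | Shift table of overall interpretation | No |
| SAP 8.7.3 | QTcF outlier counts by arm | No |
| SAP 8.7.3 | QTcF scatter plot, one panel per arm | No |
| SAP 8.1.1 | Box plots; n, mean, SD, median, minimum, maximum | No |

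SAP 8.7.6.2 does apply ANCOVA to another safety variable, endometrial thickness. SAP 8.7.6.1 (bleeding days) and 8.7.6.6 (bone biomarkers) are descriptive, like ECG.

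**2. Number per arm.** SAP 4.3 gives 95 per group, 10% dropout, SD 2.2, a difference of 1 point, two-sided alpha 0.05 and 84% power for the primary pain endpoint. No figure is stated for QTcF, so I reproduced the pain figure only to confirm the number per arm.

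- Evaluable per arm: 95 × 0.90 = 85.5.
- SE = 2.2 × √(2/85.5) = 0.336, so 1/SE = 2.97.
- Power = Φ(2.97 − 1.96) = 0.844. The t-based version gives 0.838 with 85 per arm and 0.842 with 86.

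The stated 84% reproduces. I use 86 per arm below.

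**3. Precision of one dose-minus-placebo QTcF difference at one time point.** SE = SD × √(2/86) = SD × 0.1525. Half-width = 1.96 × SE (95%) or 1.645 × SE (90%). The SD of QTcF change is an assumption, shown as a range.

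| Assumed SD (ms) | SE (ms) | 95% half-width (ms) | 90% half-width (ms) |
|---|---|---|---|
| 8 | 1.22 | 2.4 | 2.0 |
| 10 | 1.53 | 3.0 | 2.5 |
| 12 | 1.83 | 3.6 | 3.0 |
| 15 | 2.29 | 4.5 | 3.8 |
| 20 | 3.05 | 6.0 | 5.0 |

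With all 95 per arm, as is nearly the case on the first dosing day, the 95% half-widths are 2.3 to 5.7 ms for SD 8 to 20. These figures are before baseline adjustment.

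**4. Could the outlier counts do the same job?** For illustration, assume a true mean shift of 10 ms, one reading per woman, normal changes and a count of rises above 30 ms. Expected count = 86 × [1 − Φ((30 − shift)/SD)].

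| SD (ms) | Active, shift 10 ms | Placebo, shift 0 |
|---|---|---|
| 8 | 0.5 | 0.01 |
| 10 | 2.0 | 0.1 |
| 12 | 4.1 | 0.5 |
| 15 | 7.8 | 2.0 |

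SAP 8.7.3 counts women over the whole treatment period, which raises these numbers. With six post-baseline readings, within-woman correlation 0.5 to 0.7 and SD 10 (all assumed), the expected counts are about 6.5 to 8 active and 0.5 to 0.6 placebo. The count therefore depends heavily on the SD and on the number of readings. It does not estimate a mean effect.

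**The case against.** The other side has several sound points.

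- **Objective 11 names no placebo comparison.** Objectives 13 and 14, on hormones, do so explicitly, and the header calling for comparison with placebo covers the efficacy block. The planned tables answer objective 11 as it is worded. This stands.
- **Protocol 9.4.3 does not name ECG.** Safety has its own section, 9.4.7, where vital signs are descriptive, and subsection 9.4.7.3 is redacted and may address ECG. A reader might infer that the SAP plainly breaks the protocol and that its no-changes statement is false. The visible text does not establish that.
- **The information is not lost.** Protocol 9.4.1 requires summaries by treatment group, so the placebo change at the same time point will be tabulated. Subtracting two means, with an SE from the tabulated SDs and n, gives a crude contrast with about the half-widths shown above. A reader might infer that the trial cannot separate drug effect from within-day drift. It can, but without adjustment or prespecification.
- **The planned output is more than mean changes and outlier counts.** The shift table, scatter plot and box plots are also there. Nor is there support for supposing that activity differs between readings: all are taken supine after at least 5 minutes' rest.
- **The benchmarks are external.** The documents set no decision size for QTcF and no 90% convention; efficacy and PD intervals in the SAP are 95%. The 10 ms shift is only illustrative, and the actual count limits are redacted (30 and 60 appear only as plot lines). A reader might infer from one cell, such as 2 of 86 women, that outlier counts would miss a real effect. The range across assumptions is too wide for that.
- **Another plan may cover it.** SAP 7.1 and 7.2 place exposure-response modelling in a separate document. Whether that includes QTcF cannot be seen.

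What survives all of this is narrow: the SAP itself prespecifies no adjusted placebo contrast with an interval.

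**Conclusion.** The point holds as a worthwhile, low-cost improvement. SAP 8.7.3, read with 8.1.1, leaves a named safety risk and a secondary endpoint with descriptive output only. The sample already planned would support a placebo-corrected QTcF estimate for each dose to within about ±2.4 to ±6.0 ms at 95% (±2.0 to ±5.0 ms at 90%). That size rests on 86 evaluable women per arm and an assumed SD of change of 8 to 20 ms, which the sponsor should replace with its own Phase 1 or blinded value.

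The documents do not support calling this a demonstrated protocol violation, a loss of information or a failure to answer objective 11 as worded. The gain is a prespecified, baseline-adjusted estimate in place of one that each reader must assemble from the tables.

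**What to change.** Add to SAP 8.7.3:

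- A mixed model for change from baseline in QTcF, with baseline QTcF, treatment, time point (visit and pre-dose or 1.5 hours) and treatment-by-time-point. An ANCOVA at each time point, as in SAP 8.3.7, is an acceptable simpler form.
- Each dose minus placebo at every visit and time point, with a two-sided confidence interval of stated level. 95% would match the rest of the SAP; another level is acceptable if declared.
- The 1.5-hour readings named in advance as the results to highlight.
- All existing descriptive tables, outlier counts and plots kept unchanged.

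If the separate exposure-response plan already gives this estimate, a cross-reference in 8.7.3 would be enough. If descriptive reporting is deliberate, one sentence should say so and relate it to protocol 9.4.3.

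The cost is SAP wording and one model on data already collected and centrally read. The downside is a further set of nominal safety estimates without multiplicity adjustment, which should be labelled as such.
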